#### 7.4.1.2 Postoperative:

- ❶ Area under the curve of  $rSO_2$  desaturations ( $AUC_{rSO_2}$ ) of progressive categorical degrees that will include the following:
  - < 5% of established room air baseline and oxygen supplemented baseline ○ < 10% of established room air baseline and oxygen supplemented baseline ○ < 15% of established room air baseline and oxygen supplemented baseline ○ < 20% of established room air baseline and oxygen supplemented baseline ○ < 25% of established room air baseline and oxygen supplemented baseline ○ < 30% of established room air baseline and oxygen supplemented baseline

baseline ○ < 35% of established room air baseline and oxygen

supplemented baseline ○ < 40% of established room air

baseline and oxygen supplemented baseline ○ < 60% of

absolute measured value (if baseline > 60%) ○ < 55% of

absolute measured value (if baseline > 55%) ○ < 50% of

absolute measured value (if baseline > 50%) ○ < 45% of

absolute measured value (if baseline > 45%) ○ < 40% of

absolute measured value ○ < 35% of absolute measured value

○ < 30% of absolute measured value

○ < 25% of absolute measured value ○ < 20% of absolute

measured value

● Area under the curve for cumulative, high and low postoperative values outside of preestablished, individualized patient blood pressure goals based upon preoperatively observed blood pressure values as well as values clinically accepted to provide adequate organ perfusion. This analysis will be performed for systolic, diastolic and mean arterial pressures (AUCSBP-hi, AUCSBP-low, AUCSBP-cum, AUCDBP-hi, AUCDBP-low, AUCDBP-cum, AUCMAP-hi, AUCMAP-low, AUCMAP-cum). All postoperative blood pressure data will be collected with either invasive arterial catheterization [Q30 secs] or non-invasive blood pressure monitoring [Q15 min] as determined by the attending anesthesiologist caring for the subject in the PACU.

● Area under the curve of postoperative progressive categorical pulse oximetry (SpO2) desaturations (AUCSpO2) including the following:

○ AUCSpO2 < 95% regardless of intraoperative FiO2 values ○

AUCSpO2 < 90% regardless of intraoperative FiO2 values ○

AUCSpO2 < 85% regardless of intraoperative FiO2 values ○

AUCSpO2 < 80% regardless of intraoperative FiO2 values ○

$AUC_{SpO_2} < 75\%$  regardless of intraoperative  $FiO_2$  values

$AUC_{SpO_2} < 70\%$  regardless of intraoperative  $FiO_2$  values

- Time from procedure completion to arrival in the post anesthesia care unit (PACU) or ICU
- Temperature upon PACU/ICU arrival
- Aldrete score upon PACU/ICU arrival and at 30 & 60 (or at discharge) min post-PACU arrival (See Appendix A)
- Any occurrence of immediate postoperative atrial fibrillation
- Any myocardial ischemia in the immediate postoperative period
- Any need for allogeneic RBC transfusion in the immediate postoperative period
- Any observed stroke or TIA in the immediate postoperative period
- Time to clinical readiness for PACU discharge as assessed by established institutional discharge criteria (see Appendix B)
- Frequency and severity of nausea and vomiting observed in the PACU and/or ICU as assessed by an accepted postoperative nausea and vomiting scale
- ICU length of stay (ICU-LOS) [anticipated to be at least 10-20 evaluable subjects for this parameter if 100 patients are enrolled] which will be defined as time to clinical readiness for ICU discharge as assessed by the clinical team caring for the patient
- Postoperative mechanical ventilation time if still intubated and admitted to the ICU following the surgical procedure
- Use of any immediate postoperative, intravenous vasopressor and/or inotropic agent (as assessed by amount of time in minutes on any IV drug support regardless of dose and assessed by total dose of drug delivered to patient)
- Immediate postoperative urine output in any patient with an indwelling foley catheter as assessed by mLs urine/kg/hr for total time in operating room
- Hospital length of stay (H-LOS)
- Need for skilled nursing facility/rehabilitation hospital admission upon discharge from index hospitalization
- Length of time spent in a skilled nursing facility/rehabilitation hospital upon discharge from index hospitalization if a relevant data point for each subject

- Need for hospital readmission for any reason within 30 days of surgical procedure
  - Observed change from preoperative baseline Mini-mental Status Examination (MMSE) score (including postoperative day #1 and postoperative day #3 or discharge scores)
  - Presence/absence of postoperative delirium (as assessed by the CAM Delirium assessment tool results obtained preoperatively and postoperatively upon PACU discharge, Day#1 and 3 [or hospital discharge])
- Change in baseline renal function (as assessed by  $\Delta$ GFR from baseline compared to inhospital nadir postoperative GFR estimated by the Cockcroft-Galt method,  $\Delta$ preoperative serum creatinine obtained within 6 weeks of surgical procedure to nadir postoperative value and any new need for any form of renal replacement therapy)
- Postoperative use of epidural catheter
- Documented return of bowel function time (as assessed by time to first bowel movement following surgical procedure)
- Need for postoperative (any time from transfer from OR to discharge) red blood cell transfusion (as assessed by number of RBC units transfused)
- Occurrence of any postoperative (any time from transfer from OR to discharge) stroke or transient ischemic attack (as assessed by documented clinical neurological assessment or cerebral imaging study)
- Any observed postoperative (any time from transfer from OR to discharge) myocardial ischemia or infarction (as assessed by physical examination, intraoperative ECG changes and/or myocardial biomarkers [i.e. troponin increase])
- Postoperative (any time from transfer from OR to discharge) occurrence of any form infectious complication up to POD 30
- Postoperative time to wean from supplemental oxygen
- Postoperative (any time from transfer from OR to discharge) composite endpoint that includes any subject with at least one of the following: new onset atrial fibrillation,  $\geq$ Grade 2 PONV, HLOS $\geq$ 4.5 days, PACU LOS $\geq$ 2 hours, any infectious complication, death, stroke, myocardial infarction, greater 0.5 mg/dL increase in creatinine or new need for renal dialysis, postoperative need for intravenous inotropes or vasoactive medications

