  - AUCSpO2 < 80% regardless of intraoperative FiO2 values ○
  - AUCSpO2 < 75% regardless of intraoperative FiO2 values ○
  - AUCSpO2 < 70% regardless of intraoperative FiO2 values ○
- Use of any intraoperative, intravenous vasopressor and/or inotropic agent (as assessed by amount of time in minutes on any IV drug support regardless of dose and assessed by total dose of drug delivered to patient)
- Intraoperative urine output in any patient with an indwelling foley catheter as assessed by mLs urine/kg/hr for total time in operating room
- Need for intraoperative red blood cell transfusion (as assessed by number of RBC units transfused)
- Observed desaturation prompted change in surgical procedure (e.g., the surgery was paused to inflate the collapsed lung to improve systemic tissue oxygenation) ●  
● Occurrence of any intraoperative stroke or transient ischemic attack (as assessed by documented clinical neurological assessment or cerebral imaging study) ● Any

observed intraoperative myocardial ischemia or infarction (as assessed by intraoperative ECG changes and/or myocardial biomarkers (i.e. troponin increase)

- ❶ Area under the curve of any observed intraoperative hyperglycemia ( $AUC_{Glu} > 110 \text{ mg/dL}$ ) in patients with a documented history of either type I or II diabetes mellitus ❶ Any occurrence of intraoperative atrial fibrillation (capturing duration of atrial fibrillation and whether treatment was required)
- ❶ Total time spent in operating room
- ❶ Total amount of narcotic administered in the operating room
- ❶ Total volume of crystalloid administered in the operating room
- ❶ Total volume of colloid administered in the operating room
- ❶ Anti-emetic medications administered in the operating room
- ❶ Surgical procedure performed
- ❶ Time on single lung ventilation ❶

Intraoperative Use of epidural catheter

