### 9.1.1 Inclusion Criteria:

1. Any male or female patient  $\geq 65$  years of age and able to provide informed consent (or consent may be provided by a legally authorized representative) who is scheduled for a thoracic surgical procedure that is expected to involve the use of intraoperative single lung ventilation (SLV)
2. Able to adequately complete a baseline mini-mental status examination (MMSE)

3. Able to complete a baseline confusion assessment method (CAM) examination
4. Able to obtain bi-frontal baseline rSO2 values prior to induction of anesthesia

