### **11.1.3 Preoperative Variables Collected**

Following finalization of informed consent the patient's chart will be reviewed to ensure that they are appropriate for participation based upon the study's inclusion and exclusion criteria.

Additionally, the patient's records will be reviewed and key demographics and clinical variables will be collected using a standardized data collection tool. 11.1.3.1 Demographics and clinical variables collected

Age	+/- Recent MI
Gender	+/- CHF
Race	+/- DM Type II (insulin)
Height	+/- DM Type II (non-insulin)
Weight	+/- Renal Insufficiency
BMI	+/- COPD
Serum creatinine	+/- OSA
Hemoglobin	+/- Dementia
LVEF	+/- Alcohol use
+/- Vascular disease	+/- Tobacco use
+/- Stroke/TIA	+/- Illicit drug use
+/- CAD	

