### 11.2.3 MMSE and CAM Baseline Exams Performed

The mini-mental status examination and the confusion assessment method examination will be performed upon each subject to establish baseline performance prior to entering the operating room for their surgical procedure. A trained study investigator will conduct these two exams.

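### The two stand-alone atrial fibrillation endpoints count AF already present before induction; AF history, baseline rhythm and prior residence are not listed for collection, and no rule covers a positive baseline CAM

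*Combined protocol and SAP*

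**What the plan says.** **AF.** Section 7.4.1.1 lists "Any occurrence of intraoperative atrial fibrillation (capturing duration of atrial fibrillation and whether treatment was required" and section 7.4.1.2 lists "Any occurrence of immediate postoperative atrial fibrillation". Neither is limited to new episodes. The composite at the end of 7.4.1.2 is limited, to "new onset atrial fibrillation".

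**Baseline data.** Section 11.1.3 says that "key demographics and clinical variables will be collected using a standardized data collection tool". The list in 11.1.3.1 names coronary disease, heart failure, recent infarction, stroke/TIA, dementia and others. It has no AF or other arrhythmia, no rhythm, and no living situation. Table 1 has a medical history row at screening whose content is not specified.

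**Delirium.** The endpoint is "Presence/absence of postoperative delirium (as assessed by the CAM Delirium assessment tool results obtained preoperatively and postoperatively upon PACU discharge" and at later visits. Section 11.2.3 says that the MMSE and CAM "will be performed upon each subject to establish baseline performance prior to entering the operating room". The related inclusion criterion in 9.1.1 is "Able to complete a baseline confusion assessment method (CAM) examination"; a negative result is not required.

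**Facility discharge.** The endpoint is "Need for skilled nursing facility/rehabilitation hospital admission upon discharge from index hospitalization".

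**Eligibility and analysis.** Section 9.1.2 has no specific exclusion for AF, baseline delirium or facility residence. Section 15 compares the groups with a rank-sum test and defines no at-risk set and no baseline adjustment for these endpoints.

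**The concern.** A subject who enters theatre in AF meets both stand-alone AF items whichever arm is assigned. The composite shows that the investigators see the difference between new and existing AF, but the listed variables do not ensure that the two can be told apart. Elsewhere the protocol does refer outcomes to baseline: change in MMSE, change in renal function, new need for renal replacement.

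This matters because of what the pilot is for. Under 6.2 its product is a choice of outcomes that separate the arms, to be carried into a multicentre trial. Events that no intervention can move shrink the apparent effect, raise the event rates used for planning, and add noise to the choice.

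**Working it through.** **1. The definitions side by side**

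| Endpoint | Limited to new events? | Baseline fact needed | Collected? |
|---|---|---|---|
| Intraoperative AF (7.4.1.1) | No | Rhythm before induction | Not listed in 11.1.3.1 |
| Immediate postoperative AF (7.4.1.2) | No | Rhythm before induction | Not listed |
| AF within the composite (7.4.1.2) | Yes | AF history and rhythm | Not listed; Table 1 medical history may supply history |
| Delirium (7.4.1.2) | Not stated | Baseline CAM | Yes (11.2.3), but no scoring rule |
| Facility discharge (7.4.1.2) | Not stated | Residence before admission | Not listed |

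**2. Dilution, illustrated for AF**

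The plan gives no event rate, effect size or power, so there is no figure to reproduce. From the documents: 100 subjects randomised 1:1 (7.1), so 50 per arm, and a 0.05 level (section 15; two-sided assumed). Assumed: incident AF 20% vs 10% (true risk ratio 0.50), and a share q of each arm in AF throughout that always scores an event.

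Observed rate = q + (1 − q) × incident rate. For q = 10%: control 0.10 + 0.90 × 0.20 = 0.28; intervention 0.10 + 0.90 × 0.10 = 0.19; ratio 0.19/0.28 = 0.68. Existing cases as a share of control-arm events: 0.10/0.28 = 36%.

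Power uses the normal approximation Φ{[d√n − 1.96√(2p̄(1−p̄))] / √(p₁(1−p₁)+p₂(1−p₂))}, where d = p₁ − p₂ and p̄ is the mean of the two rates. The sample size per arm for 80% power is the same formula solved for n. The at-risk analysis keeps 50(1 − q) per arm at 20% vs 10%; the number to enrol is 199/(1 − q), rounded up.

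| q | Observed rates | Risk ratio | Existing share of control events | Power, all scored | Power, at risk only | N/arm for 80%, all scored | N/arm to enrol, at risk only |
|---|---|---|---|---|---|---|---|
| 0% | 20.0% vs 10.0% | 0.50 | 0% | 28.6% | 28.6% | 199 | 199 |
| 5% | 24.0% vs 14.5% | 0.60 | 21% | 22.3% | 27.4% | 270 | 210 |
| 10% | 28.0% vs 19.0% | 0.68 | 36% | 18.3% | 26.2% | 348 | 222 |
| 15% | 32.0% vs 23.5% | 0.73 | 47% | 15.5% | 25.0% | 435 | 235 |

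Other assumed incident rates, again with a true ratio of 0.50 and q = 5%, 10%, 15%: for 10% vs 5% the observed ratio is 0.67, 0.76, 0.82; for 40% vs 20% it is 0.56, 0.61, 0.65. The rarer the new event, the stronger the dilution.

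**3. Chance imbalance**

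An imbalance of 4 subjects is 4/50 = 8 percentage points.

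- *Fixed number m of existing cases among 100, split 50/50.* The SD of the between-arm difference is 2√[m × ¼ × (100 − m)/99]/50. This is 4.4 points for m = 5 and 6.0 points for m = 10. For m = 5 only odd differences can occur, so an imbalance of at least 4 means a 5-0 split: 2 × C(50,5)/C(100,5) = 0.056. For m = 10 the probability is 0.32.
- *Number of cases varying independently in each arm.* The probability of an imbalance of at least 4 is 0.105, 0.239 and 0.325 at 5%, 10% and 15% prevalence.

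**The case against.** A reader might infer that the plan counts existing disease as an outcome in all three endpoints. The text does not go that far.

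- **Delirium.** The endpoint names the preoperative CAM, every subject has one, and dementia is recorded. No sentence says that a subject positive before surgery is scored as postoperative delirium. What is missing is a rule, not data.
- **Facility discharge.** Whether going back to an existing residence counts as needing admission is not settled by the wording. The gap is that residence is not listed, so the question could not be resolved at analysis.
- **AF history.** The composite already specifies new AF, Table 1 schedules a medical history, 11.1.3 prescribes record review, and the data collection tool itself is not in the documents. AF history is unlisted; it is not shown to be unavailable.

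A reader might also infer bias between the arms. Randomisation rules that out in expectation. Nor should the 0.32 imbalance probability be taken as typical: it belongs to ten fixed cases, and five fixed cases give 0.056. The model also assumes that every existing case scores an event, which holds for subjects in persistent AF but not for everyone with a past episode. Finally, the background sections stress length of stay, stroke, organ morbidity and cognition, so nothing in the documents marks AF as a likely lead outcome.

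These objections narrow the point but do not remove it. The two stand-alone AF items, read as written, include AF present before induction, and section 15 does nothing to correct that.

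**Conclusion.** The point holds firmly for the stand-alone AF items, which disagree with the composite. For facility discharge it holds as an unlisted baseline variable, and for delirium as a missing scoring rule: a positive baseline CAM does not exclude, so it can be counted as a postoperative case.

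The consequence is dilution, chance imbalance and planning rates that are too high. Under the assumed 20% vs 10%, with 5-15% of subjects in AF throughout, a true risk ratio of 0.50 appears as 0.60-0.73 and a 20% control rate as 24-32%. A follow-on trial planned on those observed rates would call for 270-435 per arm, against 210-235 enrolled with an at-risk analysis. All of these rates are assumptions and concern AF alone; the documents offer nothing from which to size the other two endpoints.

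**What to change.** 1. Add to 11.1.3.1: history of AF, rhythm immediately before induction, and residence before admission (home or facility).
2. Define both stand-alone AF endpoints, and the composite's AF component, in one way: new AF among subjects not in AF at the pre-induction reading. Keep subjects with a past or paroxysmal history who are in sinus rhythm, because they can still have a perioperative episode; flag that history or adjust for it.
3. Define postoperative delirium as a positive postoperative CAM among subjects CAM-negative at baseline, and list baseline-positive subjects separately.
4. Define facility discharge as new placement among subjects not already living in a facility.
5. State these at-risk sets in section 15.

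The denominators then rest on facts that precede surgery and monitoring, so the randomised comparison is kept. One caution: 11.2.1 places the baseline CAM after randomisation, and a pre-induction rhythm reading would also fall there, so both should be recorded without reference to the assigned arm.

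The cost is two chart fields, one rhythm reading and slightly smaller denominators. At the assumed 5-15% in AF, about 47.5 to 42.5 subjects per arm would remain for the AF items.

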### **7 STUDY DESIGN**

#### **7.1 Study Design**

This study is a single center (University Hospitals Case Medical Center), prospective, randomized, controlled pilot study of elderly thoracic surgical patients undergoing procedures involving the use of SLV. A total of 100 eligible subjects will be randomized in a balanced fashion (1:1) to either the control cohort that will have electronically blinded bi-frontal cerebral oximetry monitoring or the intervention cohort that will have open bi-frontal cerebral oximetry monitoring with a predefined intervention protocol for observed desaturations of greater than 20% of established oxygen supplemented baseline values (see Appendix C). Both the control and intervention groups will have baseline NIRS data obtained in an unblinded fashion. The study will be divided into four separate periods that include screening, baseline acquisition, intraoperative and immediate postoperative and the postoperative follow up period.

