#### 11.4.4 Postoperative 4 Week Telephone Interview

At 4 weeks (+/- 5 days) from the day of the surgical procedure a study team member will make a telephone call to the subject with the goal of assessing overall well being, if there was any need for hospital readmission or emergency ward visit, and if applicable how many days the subject remained in a skilled nursing facility or rehabilitation hospital.

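### ICU, ventilation and nursing-facility times appear to be compared only among subjects who have them; these subsets form after randomisation, so the comparison can be biased and even change direction

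*Combined protocol and SAP*

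**What the plan says.** Three durations among the primary endpoints in Section 7.4.1.2 are worded conditionally.

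- **ICU length of stay:** "anticipated to be at least 10-20 evaluable subjects for this parameter if 100 patients are enrolled". The stay ends when the treating team judges the subject ready to leave the ICU. No value is given for a subject who never goes there.
- **Ventilation time:** "Postoperative mechanical ventilation time if still intubated and admitted to the ICU following the surgical procedure".
- **Nursing-facility or rehabilitation time:** "Length of time spent in a skilled nursing facility/rehabilitation hospital upon discharge from index hospitalization if a relevant data point for each subject". Section 11.4.4 collects it at the 4-week call: "if applicable how many days the subject remained in a skilled nursing facility or rehabilitation hospital".

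The same section also lists a yes/no endpoint that applies to every subject: "Need for skilled nursing facility/rehabilitation hospital admission upon discharge from index hospitalization". It has no matching yes/no endpoint for ICU admission or postoperative ventilation.

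Section 7.1 randomises 100 subjects 1:1. Section 11.2 places randomisation in the baseline period, before surgery. Section 15 assigns the Wilcoxon rank-sum test to between-group differences in the observed clinical data. It names no analysis set, no value for subjects without the event, and no handling of deaths.

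**The concern.** Whether a subject goes to the ICU, stays intubated or is discharged to a facility becomes known only after randomisation, and monitoring might influence it. Section 5.3 cites shorter ICU stay, and a composite that includes prolonged ventilation, among the benefits seen with this device elsewhere. If monitoring keeps milder cases out of the ICU, the intervention subjects who remain there are a sicker group than the control ICU subjects. Their stays would then look longer although the arm as a whole used less ICU time.

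This bears on the pilot's main purpose. Section 6.2 says the pilot is to find the outcome variables that diverge between arms, so that a larger trial can be designed around them. A selection effect could discard a useful endpoint or make a benefit read as harm. For ICU and ventilation time, no planned yes/no comparison would reveal the shift.

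**Working it through.** **The plan's own figure.** The 10-20 evaluable subjects is a bare expectation, 10-20% of 100, with no derivation. The documents give no power calculation, so there is nothing further to reproduce. The figure does show how ICU stay is understood: if subjects without an ICU stay counted as zero, about 100 would be evaluable, not 10-20.

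**Subset size.** 10/2 = 5 and 20/2 = 10 per arm, assuming an even split. The figure is a stated minimum and covers ICU stay only. Ventilation time is nested within the ICU subjects, so its subset cannot be larger. The size of the facility subset is not given.

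**Direction, worked example (all values assumed).** Control has 10 of 50 subjects in the ICU, five for 1 day and five for 4 days. The intervention prevents the five 1-day stays and changes nothing else.

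| | Control | Intervention |
|---|---|---|
| Mean among ICU subjects | (5×1 + 5×4)/10 = 2.5 days | (5×4)/5 = 4.0 days |
| Mean over all randomised | 25/50 = 0.50 days | 20/50 = 0.40 days |
| ICU subjects | 10/50 = 20% | 5/50 = 10% |

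The users-only rank-sum test gives p = 0.07 towards harm. The all-subject test gives p = 0.21 towards benefit.

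**Direction, simulation (assumed ICU rates).** 4,000 trials of 50 per arm were simulated, with the mildest would-be ICU cases spared and the other stays unchanged.

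| ICU rate, control v intervention | Users-only median longer in intervention arm | Users-only test significant in wrong direction | All-subject rank-sum power |
|---|---|---|---|
| 20% v 20% | 50% | 2% | no effect present |
| 20% v 10% | 86% | 17% | 25% |
| 25% v 15% | 84% | 17% | 19% |
| 15% v 5% | 92% | 14% | 35% |
| 30% v 10% | 98% | 44% | 63% |

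The first row matters as much as the others: with equal rates there is no bias. In the other four rows the average all-subject mean difference favours the intervention.

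**Sensitivity of the users-only comparison when it is unbiased.** By the two-sample t-test (two-sided 5%, 80% power), the detectable difference is 2.02 SD with 5 per arm and 1.32 SD with 10 per arm.

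**Sensitivity after the change.** In the worked example, a bootstrap 95% interval for the all-subject difference in means (control minus intervention, 0.10 days) runs from about -0.4 to 0.6 days. With assumed ICU rates of 20% v 10% and equal lognormal stays among users, all-subject rank-sum power is about 27%.

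**The case against.** **The restriction is inferred.** Section 15 does not say that only users are compared, and the collection lists in Sections 11.3.3.2 and 11.4.3.1 name ventilation, ICU and facility time without any condition. A reader might infer that the plan expressly excludes non-users for all three durations; the documents do not say that. The inference is firm for ICU stay, because of the evaluable count. It is weaker for ventilation time, and weakest for facility time, where the condition may only say when a duration is recorded. What stands is that nothing says how subjects without the event enter the test.

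**Bias needs a premise that the documents leave open.** Reversal requires monitoring to change who enters the subset. The documents do not say how ICU admission is decided. If it is settled before surgery and is unaffected by arm, the comparison is small but unbiased. The worked example also assumes the pattern that produces reversal, namely that only short stays are prevented. This objection stands, so the point is that reversal is possible.

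**Other endpoints cover everyone.** Need for facility admission, hospital stay and the composite are defined for all subjects, so a fall in facility use would be seen. This offsets much of the risk for facility time. It does not show a shift in ICU admission or ventilation.

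**It is a pilot with dozens of variables.** True, but choosing endpoints is what the pilot is for, so a selection effect in a candidate endpoint still matters.

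**Conclusion.** The concern holds in a conditional form. As worded, the plan points to a users-only comparison of ICU and ventilation time, less clearly of facility time, and has no rule for the remaining subjects. If monitoring alters who enters these subsets, the comparison can be biased and can change sign: 2.5 v 4.0 days among users against 0.50 v 0.40 days over all randomised, under assumed values. If it does not, the comparison is fair but rests on roughly 5-10 subjects per arm, assuming an even split of the stated minimum.

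Two stronger readings are not supported. One is that the arms' ICU subjects will certainly differ; that depends on how ICU admission is decided, which is not stated. The other is that using all 50 per arm brings the sensitivity a t-test would have at that size; that does not carry over to data in which 80-90% of values are zero.

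**What to change.** Add to Section 15, for ICU time, ventilation time and facility days:

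1. Make the between-arm comparison in all randomised subjects, scoring zero for survivors known to have had no use.
2. Give deaths the worst rank, or report them separately, so that an early death does not count as the best outcome.
3. Treat facility days as missing, not zero, when the 4-week call is missed.
4. Keep the rank-sum test, and report mean days per randomised subject with a bootstrap confidence interval.
5. Report the share of each arm with any ICU admission and with any postoperative ventilation, alongside the facility-admission endpoint already listed.
6. Show users-only durations as descriptive.

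The cost is a few lines of text and a little more analysis. Most zeros follow from data already collected; deaths and missed calls need the rules above. The downside is many tied zeros, so power stays modest: the change corrects what is compared and its direction, and does not promise a significant result.

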## **15 STATISTICAL PLAN**

All collected data in the case report form will be transferred into a customized electronic database upon completion of the study for the purpose of facilitating statistical analysis.

Preoperative demographics and clinical variables will be compared in the two groups to assess for significant differences using the independent t-test. Differences in the observed clinical data between groups will be determined with the Wilcoxon rank-sum test. Stepwise, forward, multivariable logistic regression analysis will be performed to assess for relationships between cerebral desaturations and any of the measured clinical variables with a p value < 0.05 being considered significant.

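### Creatinine change is taken to the lowest postoperative value, the wrong end for renal harm; separately, the MMSE and renal change comparisons make no use of the collected baselines

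*Combined protocol and SAP*

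**What the plan says.** Section 7.4.1.2 (Postoperative) includes "Observed change from preoperative baseline Mini-mental Status Examination (MMSE) score", taken at postoperative day 1 and at day 3 or discharge. It also includes "Change in baseline renal function (as assessed by" three components: the fall in estimated GFR from baseline to the in-hospital postoperative nadir, the change from "preoperative serum creatinine obtained within 6 weeks of surgical procedure to nadir postoperative value", and any new renal replacement therapy. The composite endpoint at the end of the same section counts a creatinine rise of more than 0.5 mg/dL.

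No test is attached to these endpoints individually. The general rule in Section 15, repeated in the synopsis, is "Differences in the observed clinical data between groups will be determined with the Wilcoxon rank-sum test". The only multivariable model is a stepwise logistic regression "to assess for relationships between cerebral desaturations and any of the measured clinical variables". It does not adjust the comparison between arms.

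The baselines will be available. Completing a baseline MMSE is an entry criterion (Section 9.1.1) and the test is done in every subject before the operating room (Section 11.2.3). Preoperative creatinine is recorded, together with age, weight and gender (Section 11.1.3.1).

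**The concern.** The creatinine definition looks wrong in direction. A falling GFR and a rising creatinine are the same harm, yet the plan follows both to their lowest value. An abstractor who applies the text literally would record the worst GFR and the best creatinine for the same patient.

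The analysis also leaves information unused. Subtracting the baseline fixes its coefficient at 1, whereas a model with baseline as covariate estimates it. The primary objective (Section 6.2) is to find outcomes that diverge significantly between arms, so that a larger trial can be designed around them. A noisier comparison could drop a useful endpoint, and a rank-sum p-value alone supplies no adjusted effect size or interval for planning.

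**Working it through.** **Creatinine direction.** Let c0 be the preoperative value and c1, …, cm the postoperative values.

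- Change as written: min(cj) − c0. It exceeds 0.5 mg/dL only if every postoperative value is more than 0.5 above baseline.
- Change to peak: max(cj) − c0. It exceeds 0.5 mg/dL if any value is.
- A subject whose creatinine rises by more than 0.5 and returns to c0 before discharge meets the composite criterion, but has a change to nadir of zero or less.
- With age, weight and sex fixed, a Cockcroft-type GFR estimate is inversely proportional to creatinine, so nadir GFR occurs at max(cj), not min(cj).

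The two definitions coincide only where there is a single postoperative value. Table 1 lists postoperative creatinine without saying how often it is measured.

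**Precision.** There is no planned figure to reproduce, because the 100 subjects come with no effect size, SD or power. Inputs from the plan are 100 subjects randomised 1:1 (Section 7.1), hence 50 per arm, and "with a p value < 0.05 being considered significant" (Section 15). Assumptions are a two-sided test, all 50 per arm evaluable, and a baseline–follow-up correlation r of 0.3 to 0.9.

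With a common SD of 1:

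- Var(change) = 2(1 − r)
- Var(baseline-adjusted) = 1 − r²
- Ratio = (1 + r)/2
- Smallest difference detectable with 80% power = (1.96 + 0.84) × SD of the analysed quantity × √(2/50), where √(2/50) = 0.2

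For example, at r = 0.5 the change score gives 2.80 × 1.000 × 0.2 = 0.560, and the adjusted analysis gives 2.80 × 0.866 × 0.2 = 0.485.

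| r | Variance ratio | Subjects matching 100 on change scores | Detectable difference, change (SD) | Detectable difference, adjusted (SD) | Adjusted power where change has 80% |
|---|---|---|---|---|---|
| 0.3 | 0.65 | 65 | 0.663 | 0.535 | 93.5% |
| 0.5 | 0.75 | 75 | 0.560 | 0.485 | 89.9% |
| 0.7 | 0.85 | 85 | 0.434 | 0.400 | 86.0% |
| 0.9 | 0.95 | 95 | 0.251 | 0.244 | 82.0% |

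**Unequal SDs.** With follow-up SD equal to k times baseline SD, the ratio is k²(1 − r²)/(1 + k² − 2rk).

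- k = 1.5, r = 0.7: 2.25 × 0.51/(3.25 − 2.1) = 1.1475/1.15 = 0.998
- k = 2, r = 0.5: 4 × 0.75/(5 − 2) = 1.0
- k = 0.8, r = 0.5: 0.64 × 0.75/(1.64 − 0.8) = 0.571

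The gain runs from nil to substantial and does not reverse in this large-sample formula.

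**The planned test itself.** The table uses normal theory, whereas the plan uses ranks. Power was therefore simulated with 2,000 trials per setting and 50 per arm. The three methods were rank-sum on change, linear ANCOVA, and the rank of change regressed on arm and baseline rank.

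| Setting (assumed) | Rank-sum | Linear ANCOVA | Rank of change, adjusted |
|---|---|---|---|
| Normal, r = 0.5 | 0.79 | 0.90 | 0.87 |
| Normal, r = 0.9 | 0.78 | 0.81 | 0.80 |
| Score capped at 30 (mean 28, SD 2.5), r = 0.5 | 0.87 | 0.95 | 0.94 |
| Same, r = 0.9 | 0.81 | 0.83 | 0.82 |
| Skewed, creatinine-like, r = 0.5 | 0.78 | 0.86 | 0.85 |
| Same, r = 0.9 | 0.76 | 0.77 | 0.77 |
| Heavy-tailed residuals, baseline slope 0.5 | 0.86 | 0.79 | 0.95 |
| Same, slope 0.9 | 0.91 | 0.70 | 0.92 |

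Type I error was 0.04 to 0.06 throughout. Ranking follow-up on baseline rank, rather than ranking the change, did worse than rank-sum at r = 0.9 (0.75 against 0.78 for normal data) and at slope 0.9 with heavy tails (0.76 against 0.91).

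**The case against.** On creatinine, the likeliest explanation is a drafting slip, with nadir meaning the worst renal function. The composite shows that the authors regard a rise as the harm. That explains the error but does not remove it, because the text as it stands directs the recording of the minimum.

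On precision, the other side has more. The rank-sum test on change is valid under randomisation, and this is an exploratory pilot with no power claim. The gain depends on correlations and SDs that the documents do not give. If creatinine tracks its baseline closely, the saving is about 5% of variance, and if spread widens after surgery it may vanish. Ranks also buy robustness, and linear ANCOVA gives that up when tails are heavy. All of this stands. It limits the size of the point and determines the form of the remedy.

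A reader might infer that a change score over-corrects for baseline whenever the correlation is below 1. That needs equal SDs. The relevant quantity is the slope r × k, which is 0.7 × 1.5 = 1.05 in one case above (slight under-correction) and 0.5 × 2 = 1.0 in the other (no loss). A reader might also treat MMSE as the leading neurocognitive measure. The protocol pairs it with the CAM and ranks neither first.

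**Conclusion.** The creatinine endpoint is wrong as written, whatever the correlations. It misses any rise that is not present at every postoperative measurement, and it contradicts both the GFR component beside it and the composite.

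The unadjusted comparison of MMSE, GFR and creatinine changes is an efficiency weakness and not a validity error. With equal SDs, adjustment would cut variance by 35% at r = 0.3, 25% at 0.5, 15% at 0.7 and 5% at 0.9. With a larger follow-up SD the cut can be close to zero. The pairing of change score with rank-sum is read from the general rule in Section 15, since no endpoint-specific test is named. New renal replacement therapy is a yes/no outcome and lies outside the point.

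The documents do not support the stronger inference that the planned test biases the trial, or that a linear model would be better in every case.

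**What to change.** 1. In Section 7.4.1.2, define creatinine change as the preoperative value to the peak in-hospital postoperative value. State the measurement schedule, since a maximum depends on how often creatinine is drawn.
2. In Section 15 and the synopsis, prespecify a baseline-adjusted comparison between arms for MMSE at day 1, MMSE at day 3 or discharge, postoperative GFR, and peak creatinine. Name one method per endpoint before the data are seen. Rank-based ANCOVA is suitable, best in the form that regresses the rank of change on arm and baseline rank, which fell below rank-sum in none of the simulated settings. A proportional-odds model with baseline as covariate is the alternative; it was not simulated here.
3. Report an adjusted effect estimate with a 95% CI for each, and keep the rank-sum test on change as a sensitivity analysis.

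The baseline values are already collected, so adjustment needs no new data and no extra visits. The cost is a wording amendment, plus a check that the data collection form asks for peak rather than lowest creatinine.
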